4.7.4.3 Subgroup Analyses

The primary endpoint will be explored in a number of subgroups as described in Section 4.1.5.

For each subgroup class separately, e.g. sex with classes Female and Male, the primary analysis negative binomial model will be reapplied to the primary endpoint data but now with two additional terms included, one for the subgroup, e.g. sex, and one for the interaction between the subgroup and randomised treatment. From this model, the p-value for the subgroup by randomised treatment interaction will be extracted along with estimates of the exacerbation rate ratio, colistimethate sodium:placebo, for each subgroup class, e.g. the exacerbation rate ratio, colistimethate sodium:placebo, for females and for males. The CI and p-value for these estimated exacerbation rate ratios will also be extracted and presented.

The results from all subgroups analyses will be presented in a single Forest Plot. This plot will display the treatment effect for each level of each subgroup with the associated confidence intervals and the treatment interaction p-value.

CONFIDENTIAL

Sponsor:	Zambon S.p.A.	Protocol Number:	Z7224L02
----------	---------------	------------------	----------

4.7.5 Secondary Endpoint Analysis

If the primary endpoint shows statistical significance, a hierarchical testing procedure will be applied to the secondary endpoints to provide control of the overall Type I Error. This order shall be:

- i. CCI [REDACTED]
- [REDACTED]
- [REDACTED]
- [REDACTED]
- [REDACTED]
- [REDACTED]
- [REDACTED]
- [REDACTED]
- [REDACTED]
- [REDACTED]

No test will be considered significant in this hierarchy unless every earlier test in it, including that for the primary outcome, is significant.

For the purposes of this SAP, it is anticipated that only the time to first pulmonary exacerbation and CCI [REDACTED] total scores will be analysed for the PP Population in addition to the mITT Population.

4.7.6 Methods of Analysis for Secondary Endpoints

4.7.6.1 CCI [REDACTED]

The CCI [REDACTED] will be calculated as the time in days from the date of randomisation to the date at which the first pulmonary exacerbation occurs.

- CCI [REDACTED] (days) = start date of first NCFB pulmonary exacerbation - date of randomisation. (It should be noted that this differs slightly from the CCI [REDACTED] CCI [REDACTED] CCI [REDACTED] CCI [REDACTED]. For time-to-event endpoints, generally the + 1 is not included because this overestimates the time by 1 day for every event.)

Subjects completing the trial without CCI [REDACTED] or who are discontinued prematurely CCI [REDACTED], will be considered as censored at the time of their last follow-up, i.e. at the date of treatment completion/discontinuation. For the analysis, the following formula will be applied:

- Censoring time (days) = (date of treatment completion/discontinuation - date randomisation)

The number of subjects with a first CCI [REDACTED] events will be summarised.

CONFIDENTIAL

Sponsor:	Zambon S.p.A.	Protocol Number:	Z7224L02
----------	---------------	------------------	----------

A Cox proportional hazard regression model will be applied to the data to provide an estimate of the hazard ratio (HR), colistimethate sodium:placebo. The model will include treatment group, country, as detailed in Section 4.9.1, and use of stable concomitant therapy with oral macrolides as covariates. The HR and its associated 95% CI and p-value will be extracted from the model and presented. A supportive analysis will be conducted using the log-rank test and the associated p-value will be presented.

Kaplan-Meier estimates in each treatment group will be presented: median time to CCI, 25th and 75th percentiles and the corresponding CIs will be tabulated. The number of CCI-free subjects at the beginning of the period, the cumulative number of subjects with CCI at the end of the period and the estimated rates of pulmonary exacerbations at the end of the period with the associated 95% CIs will be presented by treatment group for the following study periods: (0-28] days, (28-90] days, (90-180] days, (180-270] days and (270 days - End of Treatment] as supportive statistics.

The estimate of the survivor function in each group will be displayed graphically using a Kaplan-Meier curve.

In order to provide the best estimates of the median time to first exacerbation, a Weibull accelerated failure time model will be applied to the data using CCI. The same terms as fitted in the Cox regression analysis will be fitted in the Weibull analysis. From the Weibull analysis, estimates of the median time to first exacerbation plus 95% CI will be extracted for each randomised treatment arm along with the ratio of median times and its 95% CI and p-value.

The CCI endpoint will also be analysed in terms of subgroup 7, as explained in Section 4.1.5.

CCI *Analysis for the Effect of Concomitant Antibiotic Therapy*

A supportive analysis examining the impact of antibiotic use (by adding an additional covariate to the Cox proportional hazard regression model so that the hazard ratio is adjusted for this) will be conducted to determine if the use of antibiotics for conditions other than CCI has any impact on the CCI.

The list of medications coded to WHO-DD Preferred Terms for antibiotics and anti-pseudomonal antibiotics are included in Appendix 3. If any medication in the list has a related CCI, the response to the question CCI "?" on the CCI page for that CCI will then be checked to see whether or not the CCI in the opinion of the Investigator. If answered "No", the medication was not taken for a CCI and will be included as antibiotics used for conditions other than a CCI. Medications in the resulting list that do not have a related CCI will also be checked and included as antibiotics used for conditions other than a CCI.

Two additional tables will be presented:

CONFIDENTIAL

Sponsor:	Zambon S.p.A.	Protocol Number:	Z7224L02
----------	---------------	------------------	----------

- Supportive Cox proportional hazards analysis with use of any antibiotics for conditions other than a CCI (Yes/No) as an additional covariate.
- Supportive Cox proportional hazards analysis with use of any anti-pseudomonal antibiotics for conditions other than a protocol-defined pulmonary exacerbation (Yes/No) as an additional covariate.

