- 16) use of any intravenous or intramuscular or oral or inhaled anti-pseudomonal antibiotic (except chronic macrolides with a stable dose) within 30 days prior to the Screening Visit (Visit 1) and between Visit 1 and Visit 2;
- 17) pregnant or breast-feeding or plan to become pregnant over the next year or of child-bearing potential and unwilling to use a reliable method of contraception for at least one month before randomisation and throughout their involvement in the trial;
- 18) significant abnormality in clinical evaluations and/or laboratory tests (physical examination, vital signs, haematology, clinical chemistry, clinically relevant impaired renal function, defined as serum creatinine levels ≥ 2.0 x upper limit of normal, ECG) endangering the safe participation of the patient in the study at the Screening Visit (Visit 1) and during the study;
- 19) participated in another investigational, interventional trial within 30 days prior to the Screening Visit (Visit 1);
- 20) in the opinion of the Investigator not suitable for inclusion for whatever reason.

Contraceptive methods

Safety in human pregnancy has not been established. Animal studies do not indicate a teratogenic potential. However, there is evidence that colistimethate sodium crosses the placenta and, consequently, there is potential for foetal toxicity if administered during pregnancy.

Female subjects can be enrolled if they are either post-menopausal for at least 2 years, or surgically sterilized or have undergone hysterectomy. Female subjects of child-bearing potential must be willing to avoid pregnancy. They are required to have a negative pregnancy test at inclusion (see [Section 10.1.5](#)), and should use a highly effective method of birth control for 1 month prior to randomisation, throughout the trial duration and up to 1 month after the last dose of IMP, which include:

- combined (estrogen and progestogen containing) hormonal contraception associated with inhibition of ovulation (oral, intravaginal or transdermal)
- progestogen-only hormonal contraception associated with inhibition of ovulation (oral, injectable or implantable)

- intrauterine device
- intrauterine hormone-releasing system
- surgical sterilization (e.g. bilateral tubal ligation or occlusion)
- male sterilization (vasectomised partner)
- sexual abstinence.

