- EoT should be replaced by the last time (in days) to event >270 days (if any);

• **Tables that require Cox proportional hazards model and 95% CIs of hazard ratios between treatments:**

PROC PHREG data=dset;
CLASS treatment psite med;
*MODEL time*event(1) = treatment psite med / ties=exact;*
HAZARDRATIO 'Col. Sodium vs Placebo' treatment / cl=both;
BY byvar; (optional)
WHERE wherever; (optional)

RUN;

Notes:

- Psite represents the country, as detailed in Section 4.9.1;
- Med represents use of stable concomitant therapy with oral macrolides (e.g. azithromycin or erythromycin or clarithromycin) (Yes/No);
- Time represents the time to event or time to censoring;
- Event represents the censoring indicator (1 = censored);
- If the option ties=exact requires a considerable amount of computer resources, the Efron approximation will be used (*ties=efron*).
- Treatment order: 1= Colistimethate Sodium, 2= Placebo.

CONFIDENTIAL

Sponsor:	Zambon S.p.A.	Protocol Number:	Z7224L02
----------	---------------	------------------	----------

- **Tables that require negative binomial modelling, including 95% CIs of treatment ratios:**

```
PROC GENMOD data = dset;
  CLASS treatment psite med;
  MODEL count = treatment psite med / offset=log_years link=log dist=negbin wald
  type3;
  ESTIMATE 'Col. Sodium / Placebo' treatment 1 -1 / exp;
  lsmeans treatment / ilink cl diff exp om;
  BY byvar; (optional)
  WHERE wherever; (optional)
RUN;
```

Notes:

- Psite represents the country, as detailed in Section 4.9.1;
- Med represents use of stable concomitant therapy with oral macrolides (e.g. azithromycin or erythromycin or clarithromycin) (Yes/No);
- Count represents the total number of exacerbations for each patient;
- log_years represents the logarithm of the follow-up time in years;
- Treatment order: 1= Colistimethate Sodium, 2= Placebo.

- **Tables that require linear mixed model for repeated measures and 95% CIs of differences between treatments:**

```
PROC MIXED data = dset;
  CLASS treatment visit psite med sub;
  MODEL change = treatment visit treatment*visit psite med baseline/ s ddfm=kr;
  REPEATED visit / subject=sub type=un r;
  LSMEANS treatment treatment*visit / om at means cl slice=visit;
  LSMESTIMATE treatment
  'Col. Sodium / Placebo' 1 -1 / cl;
  LSMESTIMATE treatment*visit
  'Col. Sodium / Placebo: Visit 4' 1 0 0 0 -1 0 0 0,
  'Col. Sodium / Placebo: Visit 5' 0 1 0 0 0 -1 0 0,
  'Col. Sodium / Placebo: Visit 6' 0 0 1 0 0 0 -1 0,

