Appendix 3: WHO-DD Preferred Terms for Antibiotics and Anti-Pseudomonal Antibiotics

COMMON ANTIBIOTICS WHO PT	ANTI-PSEUDOMONAL
ADENOMYCIN	
ADICILLIN	
ALATROFLOXACIN	
AMIKACIN	Y
AMIKACIN SULFATE	Y
AMOXICILLIN	
AMOXICILLIN SODIUM;CLAVULANATE POTASSIUM	
AMOXICILLIN TRIHYDRATE	
AMOXICILLIN TRIHYDRATE;CLAVULANATE POTASSIUM	
AMOXICILLIN;CLAVULANATE POTASSIUM	
AMOXICILLIN;CLAVULANIC ACID	
AMPHOTERICIN B	
AMPICILLIN;SULBACTAM	
ASPOXICILLIN	
ASTROMICIN	
AVAROFLOXACIN	
AVIBACTAM	Y
AZIDOCILLIN	
AZITHROMYCIN	Y
AZITHROMYCIN DIHYDRATE	Y
AZTREONAM	Y
BACAMPICILLIN	
BALOFLOXACIN	
BEKANAMYCIN	
BENZYL PENICILLIN	
BENZYL PENICILLIN SODIUM	
BRODIMOPRIM	
CAFROLYCYCLINE	
CARBENICILLIN	
CARBOMYCIN A	
CARINDACILLIN	
CARUMONAM	

CONFIDENTIAL

Sponsor:	Zambon S.p.A.	Protocol Number:	Z7224L02
----------	---------------	------------------	----------

COMMON ANTIBIOTICS WHO PT	ANTI-PSEUDOMONAL
CEFACETRILE	
CEFACTOR	Y
CEFADROXIL	Y
CEFALEXIN	Y
CEFALOGLYCIN	
CEFALORIDINE	
CEFALOTIN	
CEFAMANDOLE	
CEFAPIRIN	
CEFATHIAMIDINE	
CEFATRIZINE	Y
CEFAZOLIN	Y
CEFAZOLIN SODIUM	Y
CEFEPIME	Y
CEFIXIME	Y
CEFRADINE	Y
CEFTAZIDIME	Y
CEFTAZIDIME/AVIBACTAM	Y
CEFTOLOZANE SULFATE;TAZOBACTAM SODIUM	Y
CEFTOLOZANE/TAZOBACTAM	Y
CEFTRIAZONE	Y
CEFTRIAZONE SODIUM	Y
CEFUROXIME	Y
CEFUROXIME AXETIL	Y
CHLORAMPHENICOL	
CIPROFLOXACIN	Y
CIPROFLOXACIN HYDROCHLORIDE	Y
CIPROFLOXACIN LACTATE	Y
CLARITHROMYCIN	Y
CLAVULANIC ACID	
CLINDAMYCIN	
CO-AMOXICLAV	
COLISTIMETHATE SODIUM	Y
COLISTIN	Y
COLISTIN SULFATE	Y
CO-TRIMOXAZOLE	
DORIPENEM	Y
DOXYCYCLINE	Y

CONFIDENTIAL

Sponsor:	Zambon S.p.A.	Protocol Number:	Z7224L02
----------	---------------	------------------	----------

COMMON ANTIBIOTICS WHO PT	ANTI-PSEUDOMONAL
DOXYCYCLINE HYDROCHLORIDE	Y
ERYTHROMYCIN	Y
FIDAXOMICIN	Y
FLUCLOXACILLIN	
FOSFOMYCIN	Y
FUSIDATE SODIUM	
GENTAMICIN	Y
IMIPENEM	Y
IMIPENEM/CILASTATIN	Y
LEVOFLOXACIN	Y
LINCOMYCIN HYDROCHLORIDE	
MEROPENEM	Y
MEROPENEM TRIHYDRATE	Y
METHENAMINE	
METHENAMINE HIPPURATE	
METRONIDAZOLE	
MOXIFLOXACIN	Y
MOXIFLOXACIN HYDROCHLORIDE	Y
NITROFURANTOIN	
OFLOXACIN	
PIPERACILLIN	Y
PIPERACILLIN SODIUM;TAZOBACTAM SODIUM	Y
PIPERACILLIN;TAZOBACTAM	Y
POLYMYXIN B	
ROXITHROMYCIN	Y
SULFAMETHOXAZOLE	
SULFAMETHOXAZOLE;TRIMETHOPRIM	
SULTAMICILLIN	
TAZOBACTAM	Y
TOBRAMYCIN	Y
TOBRAMYCIN SULFATE	Y
TRIMETHOPRIM	

CONFIDENTIAL

Z7224L02_SAP_v4_FINAL_08.02.2022

Final Audit Report

2022-04-08

Created:	2022-04-08
By:	PPD
Status:	Signed
Transaction ID:	CBJCHBCAABAAsB5gLhyJIPIPCdlPaFGyuXz9MfmG2OPL

"Z7224L02_SAP_v4_FINAL_08.02.2022" History

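### The supportive antibiotic-adjusted Cox analyses enter antibiotic use as a Yes/No covariate with no time window, no time-dependence and no stated exception for stable macrolides

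*SAP*

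**What the plan says.** SAP 4.7.6.1, under the analysis for the effect of concomitant antibiotic therapy, plans two extra tables. One is a "Supportive Cox proportional hazards analysis with use of any antibiotics for conditions other than a" (the next words are redacted). The other is a "Supportive Cox proportional hazards analysis with use of any anti-pseudomonal antibiotics for conditions other than a protocol-defined pulmonary exacerbation (Yes/No) as an additional covariate". The stated purpose is to learn whether such use has an impact on the endpoint, and the method is to adjust the hazard ratio "by adding an additional covariate to the Cox proportional hazard regression model so that the hazard ratio is adjusted for this". The section does not say over what period use is counted.

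The example Cox code in SAP 4.14 is for the main model: "time*event(1) = treatment psite med / ties=exact". It contains no antibiotic term and no time-varying term.

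Candidate drugs come from SAP Appendix 3. That list includes erythromycin, clarithromycin, roxithromycin, azithromycin and "AZITHROMYCIN DIHYDRATE", each flagged as anti-pseudomonal. For listed drugs without a linked record, the rule reads: "Medications in the resulting list that do not have a related CCI will also be checked and included as antibiotics used for conditions". No exception is made for stable macrolides. SAP 4.6 counts a drug started earlier and ongoing at first dose as concomitant, and SAP 3.7 asks that macrolides continue through the trial. The Cox model in SAP 4.7.6.1 already has stable macrolide use as a covariate.

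**The concern.** Antibiotic use for other conditions can begin after randomisation. A single Yes/No per patient ignores when it began, and each way of filling in the missing window causes a different problem.

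- **Use counted up to the first exacerbation or censoring.** Patients with early events have had little time to become users, so users look protected. This is immortal-time bias.
- **Use counted over all follow-up.** The model conditions on the future. A patient who starts an antibiotic after the event counts as a user before it, which dilutes any real effect.

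Two programmers could follow the same text and report quite different antibiotic hazard ratios from the same data.

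The second issue is the macrolide coding. If stable-macrolide patients are all Yes while macrolide use is its own term, they carry no information on other antibiotics.

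What is at stake is whether two planned tables can answer the question set for them.

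**Working it through.** The plan gives no figure for this analysis, so there is none to reproduce. The check is a simulation of time to first exacerbation.

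**Inputs from the documents.** 287 patients randomised (SAP 3.9). Placebo rate 1.09 per year, 35% reduction, about 20% withdrawal, 90% power with 170 completers per group (Protocol Section 3, Sample Size).

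**Assumptions not in the documents.** Other-antibiotic start rate 0.3 or 0.6 per year; 20% or 40% on macrolides; macrolide hazard ratio 0.7; true antibiotic hazard ratio 1.0 or 0.6, lasting from the start date. Withdrawal is spread uniformly. There were 300 replicates per scenario. The scenarios in which use shares patient frailty were run at 20% macrolide users only.

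**Frailty variance.** The planning variances are redacted, so k was solved from the stated power, using var(log RR) = (1/μ0 + 1/μ1 + 2k)/n:

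- μ1 = 1.09 × 0.65 = 0.7085, and ln 0.65 = −0.4308.
- 170 × (0.4308/3.2415)² = 3.003.
- 2k = 3.003 − (0.917 + 1.411) = 0.674 after rounding, so k = 0.337.

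At a 30% effect the same k gives 0.3567/0.1307 − 1.960 = 0.770, a power of 77.9% against the protocol's 80%. With the variances redacted, this gap is not evidence of an error.

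**Why the window matters.** At 0.3 starts per year, a patient with an event at one month had a 1 − exp(−0.025) = 2.5% chance of already being a user. A patient event-free at 12 months had 1 − exp(−0.3) = 25.9%. At 0.6 per year these are 4.9% and 45.1%.

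**Estimated antibiotic hazard ratio, by coding:**

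| Coding | Use unrelated to risk, true 1.0 | Use unrelated to risk, true 0.6 | Use shares frailty, true 1.0 | Use shares frailty, true 0.6 |
|---|---|---|---|---|
| Fixed, up to first event or censoring | 0.38–0.43 | 0.25–0.27 | 0.58–0.60 | 0.37 |
| Fixed, all follow-up | 0.97–1.03 | 0.80–0.83 | 1.39–1.46 | 1.15–1.19 |
| Time-dependent | 0.96–0.98 | 0.58–0.60 | 1.34–1.39 | 0.80–0.86 |

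With use unrelated to risk and a true value of 1.0, the nominal 5% test rejects in 74–99% of replicates for the first coding, 4–5% for the second and 3–5% for the third.

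A separate simulation (20,000 patients, assumed start rate 0.5 per year, antibiotics without effect) agrees. It gives 0.40 up to the event and 1.04 over all follow-up when use is unrelated to risk. When use shares frailty and is also reduced by treatment, it gives 0.61 and 1.42.

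**Macrolide coding.** With macrolide use in the model and all macrolide patients coded Yes, the flag varies only among the others. If 20% or 40% are on macrolides, a rough standard-error inflation is 1/√0.8 = 1.12 or 1/√0.6 = 1.29. The simulation gives about 10% and about 25–30%. The estimate itself hardly moves: 0.98 against 0.97, 0.81 against 0.82, 0.42 against 0.42.

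**Treatment hazard ratio.** It stays at 0.66–0.69 under every coding in the 287-patient simulation. In the larger one, where treatment also lowers antibiotic use, it moves from 0.70 to 0.67 or 0.72.

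**The case against.** The SAP calls these analyses supportive, and the hazard ratio to be adjusted is the treatment hazard ratio, which barely moves. That stands, and it limits the point to a cheap improvement.

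A reader might also infer more than the documents support:

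- **That use at any time after randomisation is what counts.** SAP 4.7.6.1 does not say so. A fixed flag is the natural reading, but the supportable statement is that no window is given. The SAP 4.14 code does not settle it, because it shows only the main model.
- **That every stable-macrolide patient will be Yes.** This is a deduction. The rule says unlinked drugs will be checked as well as included, some of its words are redacted, and a macrolide under an unlisted term would not match. The literal reading does point that way.
- **That the analysis cannot show anything about other antibiotics.** The macrolide coding does not do that. Other antibiotics are still compared among patients not on macrolides; the cost is precision and scope.

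Protocol exclusion criterion 16 sets stable macrolides apart ("except chronic macrolides with a stable dose"), but it governs eligibility, not the classification of on-study drugs. It is weak support.

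Finally, a time-dependent covariate does not remove confounding: when use shares frailty it still gives 1.34–1.39 for a true 1.0. That stands too.

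**Conclusion.** The point holds as a specification gap with a better method available. With a Yes/No flag and no window, the antibiotic hazard ratio depends heavily on a choice the SAP leaves open. For a true 1.0 it is about 0.4 if use is counted to the event, and about 1.0 if counted over all follow-up with use unrelated to risk. It is about 1.4 if counted over all follow-up with use tracking frailty. Counting over all follow-up also shrinks a true 0.6 to about 0.8. The macrolide coding, on a literal reading, adds about 10% to 30% to the standard error and confines the estimate to patients not on macrolides.

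The sizes rest on assumed antibiotic start rates, macrolide shares and effects, and on a back-solved frailty variance. The direction of the immortal-time bias does not. It would be wrong to conclude that the treatment comparison is compromised.

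**What to change.** In both supportive tables:

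1. Enter antibiotics for other conditions as a time-dependent covariate: No until the recorded start of the first such antibiotic after randomisation, Yes thereafter, with use after the first exacerbation ignored.
2. Leave stable macrolide therapy, the stratification factor, out of both flags. Its own covariate already carries it.
3. State that confounding by patient risk remains and that the antibiotic hazard ratio is not causal.

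The cost is a few lines of SAP text and start-stop records for the Cox fit. Protocol Sections 11 and 11.1 already collect start dates, end dates and reasons for use, so no new data are needed. Partial start dates need a rule; SAP 4.11 already has a missing-day rule for antibiotic courses that could be reused.

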Colistimethate sodium is an antibacterial cationic cyclic polypeptide belonging to the polymyxin group; it is currently approved in the US for intravenous administration and in Europe for both intravenous and inhaled administration. The approved injectable forms of colistimethate sodium in the US are indicated for the treatment of acute or chronic infections due to sensitive strains of certain Gram-negative bacilli and are particularly indicated when the infection is caused by sensitive strains of *P. aeruginosa*. In Europe, colistimethate sodium has been extensively used in clinical practice for over 30 years via the inhaled administration route, for the treatment of colonisation and infections of the lung by susceptible *P. aeruginosa* in patients with CF.

Colistimethate sodium (1 million International Units [MIU], equivalent to 33 mg colistin base activity [CBA]) powder for nebuliser solution has been authorized and marketed in Europe by the Zambon SpA UK affiliate (Profile Pharma Ltd) since 2003 under the brand names Promixin® and Tadim® for use in treating patients with CF who have *Pseudomonas* lung infections. The licensed dose in adults, adolescents, and children ≥ 2 years is 1-2 MIU (equivalent to 33-66 mg CBA) two to three times per day (max 6 MIU/198 mg CBA per day).

Promixin®/Tadim® (colistimethate sodium) has been authorised for nebulised treatment of colonisation and infections of the lung by susceptible *P. aeruginosa* in patients with CF since 2003. Authorisation was granted based on a bibliographic submission.

To date, two clinical studies with Promixin® (colistimethate sodium) have been completed and reported. One was a pharmacokinetic study in healthy subjects (CCI [REDACTED]),

investigating the amount of colistimethate sodium absorbed across the lungs. The second was the predecessor to the current trial (CCI [REDACTED]). This Phase 2 trial investigated the effect of inhaled Promixin® (colistimethate sodium) on time to the next pulmonary exacerbation, the effect on symptoms, and on the bacterial load in the lungs in subjects with NCFB infected with susceptible *P. aeruginosa* [14].

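### The anti-pseudomonal flag in SAP Appendix 3 is internally inconsistent and partly misclassifies exposure in one supportive Cox analysis (Table 14.2.2.2.4)

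*SAP*

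**What the plan says.** SAP Section 4.7.6.1 adds antibiotic use for conditions other than an exacerbation to the Cox model for a secondary time-to-event endpoint. Two tables follow, one for any antibiotic and one for anti-pseudomonal antibiotics. The second is described as "Supportive Cox proportional hazards analysis with use of any anti-pseudomonal antibiotics for conditions other than a protocol-defined pulmonary exacerbation (Yes/No) as an additional covariate" and is reported as Table 14.2.2.2.4 (mITT).

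The exposure is defined by reference: "The list of medications coded to WHO-DD Preferred Terms for antibiotics and anti-pseudomonal antibiotics are included in Appendix 3". Appendix 3 is a two-column list, with a preferred term and a Y where the term counts as anti-pseudomonal. Neither Section 4.7.6.1 nor the appendix says what earns a Y. Flagged rows include "FIDAXOMICIN Y", "DOXYCYCLINE HYDROCHLORIDE Y", "CEFTRIAZONE SODIUM Y", "COLISTIMETHATE SODIUM Y" and "LEVOFLOXACIN Y". Polymyxin B and ofloxacin are listed without a flag.

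Protocol Section 4 says of the study drug: "Colistimethate sodium is an antibacterial cationic cyclic polypeptide belonging to the polymyxin group". Exclusion criterion 13 likewise treats colistimethate as one of several polymyxins.

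**The concern.** The second table adds to the first only if the flag isolates drugs that act on the organism the study drug targets. If the Yes group also contains patients who took only drugs without such activity, and the No group contains some who took active ones, the covariate no longer measures what its label says. A report could then state that anti-pseudomonal co-treatment did or did not matter on the strength of a mixed exposure. The question here is only which drugs are classed as anti-pseudomonal. The timing of the covariate and the handling of stable macrolides are separate matters.

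**Working it through.** The plan gives no figure to reproduce, so the check is a count of Appendix 3 and a comparison of its rows.

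**Counts.** Appendix 3 as read has 102 terms, of which 51 carry a Y.

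**Similar rows treated differently.**

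| Flagged Y | Blank | Basis for comparing them |
|---|---|---|
| colistin, colistin sulfate, colistimethate sodium | polymyxin B | The protocol (Section 4; exclusion criterion 13) |
| ciprofloxacin, levofloxacin, moxifloxacin | ofloxacin | General pharmacology (all fluoroquinolones) |
| tazobactam alone, avibactam alone | clavulanic acid alone | All are inhibitors listed without a partner drug |
| cefalexin, cefadroxil, cefradine, cefazolin | cefalotin, cefapirin, cefaloridine | General pharmacology (older cephalosporins) |

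Seven cephalosporins are blank in all: cefacetrile, cefaloglycin, cefaloridine, cefalotin, cefamandole, cefapirin and cefathiamidine.

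**Flagged terms not generally regarded as active against *P. aeruginosa*.**
- Cephalosporins: the row printed CEFACTOR (presumably cefaclor) 1, cefadroxil 1, cefalexin 1, cefatrizine 1, cefazolin 2, cefixime 1, cefradine 1, the rows printed CEFTRIAZONE (presumably ceftriaxone) 2, cefuroxime 2. Total 12.
- Doxycycline 2.
- Fidaxomicin 1.

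12 + 2 + 1 = 15, and 15/51 = 29%. The other 51 − 15 = 36 flags are not disputed in this count, although moxifloxacin and the inhibitor-only terms among them still need review. In the other direction, polymyxin B, ofloxacin, carbenicillin and carindacillin are blank and need review.

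**Spelling.** If CEFACTOR and CEFTRIAZONE are printed as they stand in the look-up, and the program matches exact text, those three rows may match no coded record. The disputed share of operative flags would then be 12/48 = 25%, and those drugs would also be missed by the any-antibiotic list. If the spellings are typing or PDF-reading errors, nothing follows from them.

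**What this does to the covariate.** Suppose a fraction *p* of the Yes group took only drugs with no effect on the outcome. The covariate's log hazard ratio is then roughly (1 − *p*) times its value under a clean flag. The documents do not give *p*, and it could in principle lie anywhere from 0 (no dilution) to 1 (complete dilution). The 29% is a share of list entries and does not estimate *p*.

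**Which analyses use the flag.** Table 14.2.2.2.4 does. The primary negative binomial model (SAP 4.7.4), the main Cox model (SAP 4.7.6.1) and the any-antibiotic covariate do not.

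**The case against.** The strongest reply is that most of this rests on microbiology the documents do not contain. They nowhere say that doxycycline, the listed cephalosporins or fidaxomicin lack activity against *P. aeruginosa*, or that ofloxacin has it. They also seem to use the term broadly: exclusion criterion 16 has to carve out stable macrolides from anti-pseudomonal antibiotics, and Appendix 3 flags macrolides too. The list might therefore be a deliberately wide operational one. The inhibitor rows may even follow a rule, since the appendix pairs tazobactam and avibactam with flagged partner drugs and clavulanate only with amoxicillin. This stands in part. The status of the 15 terms needs confirming by someone qualified, and what is plainly missing is a stated criterion. But a wide rule does not explain polymyxin B, which is blank beside three flagged members of its own group.

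A reader might infer that the analysis runs on the wrong exposure altogether, or that it collapses into the any-antibiotic table. The appendix does not support that. Ceftazidime, cefepime, meropenem, piperacillin, tobramycin and ciprofloxacin are flagged. Every amoxicillin term, flucloxacillin, trimethoprim, nitrofurantoin and metronidazole are blank. The two covariates remain different.

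A reader might also infer that the treatment hazard ratio in this table is materially biased. The documents do not show that either. If use of these drugs is similar in the two arms, re-coding the flag should move the adjusted treatment effect little. Use that differs by arm could change this, but the documents give no counts.

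**Conclusion.** The concern holds, at minor severity. The column that alone defines the covariate contradicts itself and partly misclassifies exposure, so Table 14.2.2.2.4 cannot cleanly show whether anti-pseudomonal use affected the result. The polymyxin inconsistency rests on the documents alone. The 15 of 51 terms rest on general microbiology, subject to the medical monitor's confirmation. The effect on the covariate's coefficient and on the treatment hazard ratio cannot be computed, and the 29% should not be read as a share of patients or as a percentage bias. The documents do not show that any subject took polymyxin B, carbenicillin or carindacillin. Only one supportive table of a secondary endpoint is affected.

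**What to change.** While the trial is still blinded, have the medical monitor or a microbiologist re-code the Appendix 3 column under one written criterion, such as established activity against *P. aeruginosa*. In particular:
- reconcile polymyxin B with colistin, and ofloxacin with levofloxacin;
- review the 15 terms listed above, carbenicillin, carindacillin, the inhibitor-only terms and moxifloxacin;
- check that CEFACTOR and CEFTRIAZONE match the coded preferred terms, since this bears on both antibiotic tables.

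Then run Table 14.2.2.2.4 on the corrected flag. If the blind is already broken, SAP Section 1 gives the route: document and justify the change in the clinical trial report and mark it as post hoc. The cost is one look-up column and one short expert review, with no new data and no change to the primary analysis.
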